### 7.4.2 Tipping Point Analyses

The Tipping Point method will be adopted to further evaluate study primary objectives by assessing the impact of missing or unknown outcome data on study results. Tipping point analysis results for both primary effectiveness endpoint and primary safety endpoint will be reported.

## 7.5 Adjustments for Multiple Comparisons

No adjustment for multiple comparisons is needed for this study as both primary endpoints need to be passed for study success.

## 7.6 Demographic and Other Baseline Characteristics

Demographic (e.g. age, gender, race, etc.) and other baseline characteristics will be summarized descriptively.

## 7.7 Treatment Characteristics

Procedural characteristics, concomitant therapies and medications will be summarized descriptively.

## 7.8 Interim Analyses

No interim analysis is planned which would be intended to alter the study sample size or terminate the study early.

## 7.9 Evaluation of Objectives

### 7.9.1 Primary Effectiveness Endpoint

Primary Patency is defined as meeting all of the following criteria at 12 months post-procedure:

---

- Freedom from occlusion of the stented segment of the target lesion;
- Freedom from restenosis  $\geq 50\%$  of the stented segment of the target lesion;
- Freedom from clinically-driven target lesion revascularization

All subjects will undergo DUS assessments for determination of patency.

An additional venogram must be performed when:

- (1) DUS assessment is suggestive of  $\geq 50\%$  restenosis or occlusion per investigator assessment, or
- (2) when DUS is non-diagnostic or suboptimal such as when a patient is obese (e.g. with a BMI  $>40$ ), or
- (3) is clinically required, or in other words when the patient is having symptoms of venous disease in the target limb requiring a venogram. All DUS and venographic imaging examinations will be analyzed by respective independent core laboratories.

Clinically driven is defined as the recurrence of symptoms present at baseline or the onset of new symptoms including, but not limited to venous pain, swelling, dermatitis, or ulceration related to the target limb.

Clinically driven target lesion revascularization will be adjudicated by the CEC based on core laboratory adjudicated imaging data and relevant clinical information provided by the site.

### 7.9.1.1 Hypothesis Testing

The primary effectiveness endpoint in this study is primary patency rate. The statistical hypothesis on this endpoint is that primary patency through 12 months will exceed a performance goal established from historical literature references using venous stenting as the treatment of choice. Formally, the null and alternative hypotheses to be tested appear below:

$$H_0: \pi \leq PG$$

$$H_A: \pi > PG$$

where  $\pi$  is the primary patency rate at 12 months in the study population and PG is the performance goal of 75%.

### 7.9.1.2 Statistical Method

The primary patency rate is calculated as the number of subjects without loss of primary patency divided by the number of subjects having evaluable primary endpoint data for primary patency rate at 12 months.

Based on the literature (see ABRE CIP Appendix A Scientific Literature Search), the weighted mean expected primary patency was 85.7%. By subtracting a margin of indifference of 10% from expected performance ( $85.7\% - 10\% = 75.7\%$ ); consequently, the value of 75% is therefore taken as the performance goal for the current study. The 12-month patency rate and lower limit of the 97.5% one-sided confidence interval will be reported. The primary effectiveness objective will be met if the lower limit of the 97.5% one-sided confidence interval of the 12-month patency rate is above 75%.

For the primary effectiveness endpoint, subjects will be included in the analysis and considered evaluable if:

- (a) the subject experiences at least one clinically-driven target lesion revascularization within 390 days;
- or (b) the subject has occlusion or restenosis  $\geq 50\%$  of the stented segment of the target lesion confirmed by core laboratory at 12 months or
- (c) the subject has at least 330 days follow up without an event in the primary effectiveness endpoint.

For analysis of the imaging component of primary patency, if a subject has both a valid venogram and DUS during the 12-month follow-up period then the venogram will be used. If no venogram is available,

then the DUS will be used. This is an imaging endpoint. More details of the reporting rules are used to determine this endpoint can be found in section 10.3.2.

Further, as supportive analysis on the primary endpoints, time-to-event analysis for primary patency through 12 months will also be performed and serves as a secondary analysis. Kaplan-Meier (KM) estimates with 95% two-sided confidence interval using Peto formula will be reported for primary patency rate through 360 days as well as 390 days to accommodate the 12-month visit window. Subjects not experiencing the event by 12 months will be censored at 12 months or last known follow-up as defined in Appendix A, whichever is earlier. Subjects not experiencing the CD-TLR but experiencing the Target Vessel Revascularization (TVR) before 12-month imaging window will be censored at date of TVR when evaluating the 12-month primary effectiveness endpoint. The imaging assessment for such subjects that are available either on or before the TVR date, if within the 12-month reporting window, may still be used.

Sensitivity analyses for primary effectiveness endpoint include multiple imputation and tipping point analysis which are further explained in section 7.4.

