## 14.2 Sample Size Calculation

**Primary Effectiveness:** Using the assumptions above on the performance goal and anticipated outcome, we assume desired power of at least 92% under difference testing relative to the performance goal at a one-sided alpha of 0.025. The resulting evaluable sample size required is then 160 subjects using exact binomial test for a single proportion. Accounting for attrition during follow-up, the sample size is augmented by 20% to 200 subjects. Every effort will be made, however, to minimize loss to follow-up.

**Primary Safety:** Using the assumptions above on the performance goal and anticipated outcome, we assume desired power of at least 92% under difference testing relative to the performance goal at a one-sided alpha of 0.025. The resulting evaluable sample size required is then 193 subjects using exact binomial test for a single proportion. Accounting for attrition during follow-up, the sample size is augmented by 3.5% to 200 subjects. Every effort will be made, however, to minimize loss to follow-up.

In summary, the overall power of the study is at least 84% while the effectiveness and safety performance goals are as follows:

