## 14.3 Analysis Sets

The primary analysis set will consist of all subjects who were enrolled and had the Abre system introduced into the vasculature. In general, all analyses will be performed using all evaluable subjects for primary effectiveness and safety analyses (evaluable subject definitions provided below).

The PMA primary analysis will occur when all 12-month follow-up data have been collected.

For the primary effectiveness endpoint, subjects will be included in the primary analysis when:

- a) the subject experiences at least one clinically-driven target lesion revascularization within 390 days; or
- b) the subject has occlusion or restenosis  $\geq 50\%$  of the stented segment of the target lesion confirmed by core laboratory at 12 months visit; or
- c) the subject has at least 330 days follow up without an event in the primary effectiveness endpoint.

For the primary safety endpoint, subjects will be included in the primary analysis when:

- a) the subject experiences at least one of the primary safety composite events within 30 days; or
- b) stent-migration and stent thrombosis confirmed by imaging as assessed by core laboratory at 30-day visit; or
- c) the subject has at least 23 days of clinical follow up without an event in the primary safety endpoint.

Secondary analyses for primary safety endpoint will be conducted on all implanted subjects in whom the denominator for the primary safety endpoint will be the number of implanted subjects who had sufficient follow up (at least 23 days for 30-day visit) plus any subjects who had an event prior to the 30-Day Follow-Up visit.

One interim analysis will be performed on safety for the DSMB. The interim analysis is planned when 30-day follow-up data have been obtained on 30 subjects. The interim analysis does not permit early stopping for effectiveness and therefore no alpha-spending or other adjustment to the study's statistical hypotheses is required. The DSMB Charter may specify additional safety analyses.

Additional exploratory analyses of the data may be conducted as deemed appropriate.

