Adverse occurrences beyond 30 days were also tabulated and included Target Lesion Revascularization (TLR), stent fracture and stent migration. TLR occurred in 8.3% of patients overall through 12 months, and appeared most common in post-thrombotic cases (13.1%). Stent fracture was reported in 1.4% of patients. Stent dislodgement and stent migration were observed in 0.6% and 1.6% of cases, respectively (including migration beyond 30 days).

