## 6.3 Sample Size Calculation

Primary Effectiveness: Using the assumptions above on the  $PG$  and anticipated outcome, we assume desired power of at least 92% under hypothesis testing relative to the performance goal at a one-sided alpha of 0.025. The resulting evaluable sample size required is then 160 subjects using exact binomial

test for a single proportion. Accounting for attrition during follow-up, the sample size is augmented by 20% to 200 subjects. Every effort will be made, however, to minimize loss to follow-up.

Primary Safety: Using the assumptions above on the performance goal and anticipated outcome, we assume desired power of at least 92% under hypothesis testing relative to the PG at a one-sided alpha of 0.025. The resulting evaluable sample size required is then 193 subjects using exact binomial test for a single proportion. Accounting for attrition during follow-up, the sample size is augmented by 3.5% to 200 subjects. Every effort will be made, however, to minimize loss to follow-up.

In summary, the overall power of the study is at least 84% while the effectiveness and safety PGs and the projected rates needed to achieve them are as follows:

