1. CD-TLR
2. Imaging endpoint of Occlusion/Restenosis

Primary patency endpoint determination will follow the rules described below:

1. Censor any imaging assessments or events after any TVR (not clinically driven) as this changes the vessel making the subject unevaluable for patency at 12 months. If the date of assessment > date of TVR, then set the value to 'missing'
2. All Subjects that had CD-TLRs within 390 days will be counted as Primary Patency Failure whether or not an imaging assessment is available after the CD-TLR event. Subjects with TVR (not clinically driven) before the CD-TLR will be censored.
3. The imaging component of the 12-month primary patency will be constructed based on 'AT' principle – prior events will not be carried over to a later visit. For each subject, qualified imaging assessment will be determined in the following order:
  - a. Venogram on scheduled 12-month visit regardless of window.
  - b. DUS on scheduled 12-month visit regardless of window
  - c. Venogram from unscheduled visit within the imaging window, choose the one closest to the target visit date if there are multiple
  - d. DUS on unscheduled visit within the imaging window, choose the one closest to the target visit date if there are multiple

Primary Patency at 24 months, and 36 months follow-up will be determined following the similar convention specified above for 12 months.

For each individual component of the primary patency endpoint, the rate will be calculated in the following way:

The proportion rate of CD-TLR will be constructed as a clinical/safety endpoint - number of subjects with CD-TLR over number of evaluable subjects through the cutoff of a reporting time point. For example, for 12-month CD-TLR under the primary patency endpoint, the cutoff to determine the numerator is 390 days – this includes any subjects who had their first CD-TLR within 390 days. The denominator will be all subjects that had CD-TLR or had no CD-TLR but had at least 330 days of clinical follow-up.

The CD-TLR Endpoint will be reported cumulatively.

The determination of imaging component of the occlusion/restenosis endpoint is described above.

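### At the planned 20% loss, the evaluability rule keeps CD-TLR failures but drops event-free subjects lost before day 330, so effectiveness power is about 86-89% under the exact test, not at least 92%

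*SAP*

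**What the plan says.** SAP 7.9.1.2 and protocol 14.4.1 define the primary rate as subjects without loss of patency over subjects with evaluable 12-month data. Success requires the lower one-sided 97.5% confidence limit to exceed 75%.

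SAP 7.1.3, SAP 7.9.1.2 and protocol 14.3 give three routes to being evaluable:

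- (a) "the subject experiences at least one clinically-driven target lesion revascularization within 390 days";
- (b) occlusion or restenosis of at least 50%, confirmed by the core laboratory at 12 months;
- (c) "the subject has at least 330 days follow up without an event in the primary effectiveness endpoint".

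SAP 10.3.2.2 makes (a) unconditional on imaging: "All Subjects that had CD-TLRs within 390 days will be counted as Primary Patency Failure whether or not an imaging assessment is available". Under the same section, imaging failures are judged at the 12-month assessment only and earlier findings are not carried forward.

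On sample size, SAP 6.3 says "we assume desired power of at least 92% under hypothesis testing relative to the performance goal at a one-sided alpha of 0.025". It continues: "The resulting evaluable sample size required is then 160 subjects using exact binomial" testing, and for attrition "the sample size is augmented by 20% to 200 subjects". The PASS output prints power 0.9288 at n = 160 and patency 85.7%. Protocol 14.2 concludes: "In summary, the overall power of the study is at least 84" per cent. The synopsis and SAP section 3 say at least 80%.

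The Kaplan-Meier analysis is secondary (SAP 7.9.1.2). Multiple imputation and tipping point are sensitivity analyses (SAP 7.4, 7.9.1.2). None of these decides success.

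**The concern.** Applying 85.7% to the 160 remaining subjects is valid only if being evaluable is unrelated to outcome. Under criteria (a) and (c) it is related. Take two subjects who leave at month 8. The one with a CD-TLR at month 3 stays in the denominator as a failure. The event-free one disappears. Subjects whose failure would have shown only on the 12-month image are lost at the same rate as successes. The ratio is therefore pulled toward failure by loss that has nothing to do with prognosis.

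Two things are at stake. The stated power would not be delivered at the plan's own attrition figure, and the reported rate would understate 12-month patency. SAP 10.3.2.2 also applies a similar convention at 24 and 36 months, where cumulative loss can be larger.

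**Working it through.** **1. The printed design reproduces.** Exact test, n = 160, null 75%, alternative 85.7%: reject at 131 or more, alpha 0.0247, power 0.9288. 160/(1 − 0.20) = 200. The printed safety power is 0.9233, and 0.9288 × 0.9233 = 0.858. The printed figures are arithmetically right for 160 evaluable subjects when loss is unrelated to outcome. Letting the evaluable number vary around 160, as it does when each of 200 subjects has a 20% chance of loss, gives 0.914.

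**2. Inputs for the rule as written.** N = 200 and loss 0.20 (SAP 6.3). Total failure is 1 − 0.857 = 0.143. The documents give no CD-TLR rate. Protocol Appendix A reports that "TLR occurred in 8.3% of patients overall through 12 months", which counts any TLR, so CD-TLR is assumed at c = 8.3%, 6% or 4%. Timing is also an assumption: loss uniform over days 0-330 and CD-TLR uniform over days 0-360. For a subject who is lost, the chance that the CD-TLR came first is u = 165/360 = 0.458.

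**3. Formulas.**

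- Patent and evaluable: 0.857 × 0.80 = 0.6856
- Image-only failure and evaluable: (0.143 − c) × 0.80
- CD-TLR failure and evaluable: c × [1 − 0.20 × (1 − 0.458)] = c × 0.892
- q = the sum of the three; expected rate = 0.6856/q; evaluable number ~ Binomial(200, q). The exact critical value is applied at each evaluable number.

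| CD-TLR | CD-TLR kept | Image-only kept | q | Expected n | Expected rate | Power | × 0.9233 |
|---|---|---|---|---|---|---|---|
| 8.3% | 0.0740 | 0.0480 | 0.8076 | 161.5 | 84.9% | 0.860 | 0.795 |
| 6% | 0.0535 | 0.0664 | 0.8055 | 161.1 | 85.1% | 0.877 | 0.810 |
| 4% | 0.0357 | 0.0824 | 0.8037 | 160.7 | 85.3% | 0.890 | 0.822 |

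A time-based simulation of the 8.3% case gave a rate of 84.9% and power of 0.862. Against the 0.914 comparator, the rule itself costs about 5, 4 and 2 points.

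**4. Smaller loss.** At c = 8.3%, the same calculation gives power of about 0.90 at 15% loss, 0.93 at 10% and 0.95 at 5%.

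**5. False success.** Take true patency of 75% with the same CD-TLR share of failures (8.3/14.3 = 58%). The expected observed rate is then about 73.8% and the one-sided error about 0.8%, below 2.5%.

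**6. Missing images instead of early loss.** Suppose the whole 20% is missing 12-month images.

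- If event-free subjects without an image are excluded, every CD-TLR is kept. At c = 8.3% the rate is 0.6856/(0.6856 + 0.048 + 0.083) = 84.0% and power is 0.778. Power is 0.823 at 6% and 0.857 at 4%.
- If criterion (c) is taken literally, they count as patent once they have 330 days of follow-up. The rate is then 0.857 + 0.20 × 0.060 = 86.9% on 200 subjects, and power is 0.988. At true patency of 75%, image-only failures are 0.25 − 0.145 = 0.105, so the counted rate is 0.75 + 0.20 × 0.105 = 77.1%. The chance of reaching the critical value of 163 out of 200 is about 0.079.

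**The case against.** **The printed power is correct for what it states.** It is power at 160 evaluable subjects, 20% is a planning allowance, and the plan commits to minimising loss. This stands in part. There is no arithmetic error, and at 10% loss the stated figure is met. But the plan links 160 to 200 through a 20% loss, and at that loss its own rule does not deliver the figure.

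**The CD-TLR rate is weak.** This stands. The 8.3% is any TLR, and Appendix A Table XII has no TLR figure for non-thrombotic series, whose 12-month patency was highest (94.8%). SAP Table 5 also sets a TLR that was not clinically driven to missing, whereas the review counted any reintervention as loss of patency. That is an offset not quantified here. Hence the 4-8.3% range.

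**Timing.** If dropout reaches 20% only at day 365, the same curve has lost about 18.3% by day 330, and power is about 88-90%. This is milder but still below 92%.

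**The interval method is unnamed.** The exact method is specified for safety only. With a Wald limit (observed rate − 1.96 standard errors), the three cases in the table give 0.910, 0.922 and 0.931, against 0.948 under outcome-independent loss. The bias in the rate is unchanged, but the stated power would be met or nearly met. The exact test is used here because the sample size calculation uses it.

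**A stronger reading.** A reader might infer power of 78% and overall power of 72%. The documents do not establish that. It requires the full 20% to be missing images and event-free subjects without an image to be excluded. SAP Table 5 has no row for a missing image without CD-TLR, and criterion (c) read literally would count such subjects as patent. SAP 10.3.2.2 (a qualified image) and the synopsis (evaluable patency data) point toward exclusion, so the text is ambiguous.

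**Conclusion.** The concern holds in this form. With 20% of 200 subjects lost evenly by day 330, true patency of 85.7%, loss unrelated to prognosis and the exact test, the expected observed rate is about 84.9-85.3%. Effectiveness power is about 86% (CD-TLR 8.3%), 88% (6%) or 89% (4%), not at least 92%. With safety power left at 92.3%, overall power is about 80-82%. That is below the at-least-84% of protocol 14.2 and close to the at-least-80% of the synopsis.

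The shortfall is small at 10% loss or less. A reader might infer that a positive result is unsafe. Loss to follow-up under this rule does not support that, because the bias is toward failure. The exception is the literal reading of criterion (c) for subjects still in contact but not imaged, where the direction reverses. One-directional bias therefore cannot be asserted until that criterion is clarified.

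**What to change.** 1. **SAP 6.3 and protocol 14.2:** restate effectiveness and overall power at 20% loss, naming the assumed CD-TLR rate, the timing of loss and the interval method.
2. **SAP 7.9.1.2 and protocol 14.3:** make criterion (c) require a qualified 12-month core-laboratory image, consistent with SAP 10.3.2.2, so that unimaged subjects are not counted as patent. Align SAP 7.1.3 and add the missing row to Table 5.
3. **Reporting:** give the crude rate with a note that, under that reading, differential evaluability biases it toward failure.
4. **Supportive analysis, labelled post hoc:** Kaplan-Meier freedom from CD-TLR through day 390, times the proportion patent among imaged CD-TLR-free subjects. State how non-clinically-driven revascularization is censored. In simulation at 20% loss this estimate averaged 0.857 in both the dropout and the missing-image scenarios.

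The product estimate should not replace the primary estimator. The marketing application was submitted on all available 12-month data and approved before protocol version 2.0, so a switch now would be a post hoc move to an estimator more likely to pass.

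The cost is wording and a few lines of code, with no new data or subjects. The stated power becomes less favourable, and requiring an image lowers the evaluable number wherever images are missing. If the 12-month analysis already reported used another reading of criterion (c), the report should say so.

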#### **Primary effectiveness endpoint**

Primary Patency is defined as meeting all of the following criteria at 12 months post-procedure:

- Freedom from occlusion of the stented segment of the target lesion;
- Freedom from restenosis ≥50% of the stented segment of the target lesion;
- Freedom from clinically-driven target lesion revascularization

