**Table 5. Primary Assisted Patency and Secondary Patency Endpoints**

Outcome Scenarios	Primary Patency	Primary Assisted Patency	Secondary Patency
Patent (DUS, Venogram) at 12 months, no CD-TLR and no TLR before 12 months	Success	Success	Success
Binary Restenosis/Occluded (DUS, Venogram) at 12 months, and no TLR (not clinically driven) before 12 months	Failure	Failure	Failure
TLR (not clinically driven) before 12 months, before any CD-TLR , before 12 month imaging	Missing	Missing	Missing
Patent Venogram, DUS) at 12 months, CD-TLR before 12 months due to restenosis but no occlusion	Failure	Success	Success
Patent (Venogram, DUS) at 12 months, CD-TLR before 12 months due to occlusion	Failure	Failure	Success
Image missing at 12 months, CD-TLR before 12 months due to restenosis but no occlusion	Failure	Missing	Missing
Image missing at 12 months, CD-TLR before 12 months due to occlusion	Failure	Failure	Missing

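### SAP 10.3.2.2 and Table 5 use different re-intervention triggers for setting primary patency to Missing, and TVR is undefined, so one subject can be classified two ways; this decides the result only near the pass line

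*SAP*

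**What the plan says.** The protocol (6.3.1) defines primary patency at 12 months on the stent: no occlusion and no restenosis "≥50% of the stented segment of the target lesion", and no CD-TLR. Appendix B of the protocol limits TLR to re-intervention in the stented segment. It defines the target vessel as the common iliac, external iliac and/or common femoral vein. TVR is spelled out once in SAP 7.9.1.2, is absent from the SAP abbreviation list, and is defined in neither document.

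The SAP describes the effect of a re-intervention on primary patency in three places:

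- **SAP 10.3.2.2, rules 1 and 2** (the determination rules for the composite). Rule 1: "Censor any imaging assessments or events after any TVR (not clinically driven"), because the vessel has changed; later assessments become missing. Rule 2 counts every CD-TLR within 390 days as a failure, then censors subjects who had such a TVR before the CD-TLR.
- **SAP Table 5, Primary Patency column.** Row 1, "Patent (DUS, Venogram) at 12 months, no CD-TLR and no TLR before 12 months", is Success. Row 2, restenosis or occlusion at 12 months without a not clinically driven TLR, is Failure. Row 3, a not clinically driven TLR before any CD-TLR and before the 12-month image, is Missing. TVR does not appear.
- **SAP 7.9.1.2, Kaplan-Meier paragraph.** "Subjects not experiencing the CD-TLR but experiencing the Target Vessel Revascularization (TVR) before 12-month imaging window will be censored at date of TVR", with no clinically driven qualifier. The sentence says it applies to the 12-month primary effectiveness endpoint. The next sentence allows images from on or before the TVR date to be used if they fall in the 12-month reporting window.

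The evaluability criteria (protocol 14.3; SAP 7.1.3 and 7.9.1.2) exclude nobody for a re-intervention. Criterion (a) admits any subject with a CD-TLR within 390 days. Criterion (c) requires that "the subject has at least 330 days follow up without an event in the primary effectiveness endpoint".

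**The concern.** Because the target vessel is wider than the stented segment, a re-intervention can be a TVR without being a TLR. For such a subject the SAP sections give different answers, so the numerator and denominator of the primary proportion depend on which section is programmed. By the time that choice is made, the 12-month images and the adjudicated clinically driven status are known. The ambiguity can remove patent subjects or failed subjects, so it has no fixed direction.

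Rule 1 also creates a follow-on gap. A subject it sets to missing, but who was followed for 330 days without an event, still satisfies criterion (c). The text of SAP 7.4.1 does not settle whether the multiple imputation covers that subject.

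**Working it through.** **1. Classification.** Take a subject with a re-intervention in the target vessel outside the stent, before the 12-month image.

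| Off-stent TVR, then | SAP 10.3.2.2 | SAP Table 5 | SAP 7.9.1.2 Kaplan-Meier sentence |
|---|---|---|---|
| Not clinically driven; patent image | Missing (rule 1) | Success (row 1) | Censored |
| Not clinically driven; in-stent restenosis on image | Missing (rule 1) | Failure (row 2) | Censored |
| Not clinically driven; CD-TLR within 390 days | Censored (rule 2), yet evaluable under criterion (a) | Failure (CD-TLR rows) | Not addressed (sentence covers only subjects without CD-TLR) |
| Clinically driven; patent image | Success (rule 1 not triggered) | Success (row 1) | Censored |

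The first three rows conflict without any help from the Kaplan-Meier sentence.

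**2. Inputs for the size.** The test uses a "one-sided alpha of 0.025" (SAP 6.3). For the null, "PG is the performance goal of 75" per cent (SAP 7.9.1.1). For planning, "the weighted mean expected primary patency was 85.7" per cent (SAP 7.9.1.2). The evaluable n is 160 with an exact binomial test (SAP 6.3). Success requires the one-sided 97.5% lower limit (LCL) to exceed 75%.

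**3. The plan's own figure.** For X ~ Bin(160, p): P(X ≥ 131 | p = 0.75) = 0.0247 and P(X ≥ 131 | p = 0.857) = 0.9288. Both match the sample-size output in SAP 6.3 (alpha 0.0247, power 0.9288, reject at 131 or more).

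**4. Lower limit.** SAP 7.9.1.2 does not name an interval method for effectiveness. I use the exact (Clopper-Pearson) limit, which corresponds to the exact test: LCL = the 0.025 quantile of Beta(x, n − x + 1).

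**5. Patent subjects moved from Success to Missing** (k leaves both x and n):

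| Start | LCL | Smallest k that fails | Result | LCL |
|---|---|---|---|---|
| 131/160 | 75.02% (met) | 1 | 130/159 | 74.87% (not met) |
| 132/160 | 75.71% (met) | 5 | 127/155 | 74.96% (not met) |
| 163/200 | 75.41% (met) | 4 | 159/196 | 74.93% (not met) |
| 137/160 (planning rate) | 79.22% (met) | 29 | 108/131 | 74.83% (not met) |

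Six removals at the planning rate give 131/154, LCL 78.4%, still met. The estimate moves from 137/160 = 85.6% to 131/154 = 85.1%.

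**6. Failed subjects moved from Failure to Missing** (k leaves n only):

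| Start | LCL | Smallest k that passes | Result | LCL |
|---|---|---|---|---|
| 130/160 | 74.33% (not met) | 2 | 130/158 | 75.42% (met) |
| 129/160 | 73.64% (not met) | 3 | 129/157 | 75.27% (met) |
| 128/160 | 72.96% (not met) | 4 | 128/156 | 75.11% (met) |

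The documents give no TVR frequency, so these counts are thresholds, not forecasts.

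**The case against.** The strongest reply is that the SAP has one operative rule. Section 7.9.1.2 sends the reader to 10.3.2 for the determination of the endpoint, and 10.3.2.2 carries that title. The Kaplan-Meier sentence belongs to an analysis labelled supportive and secondary, and Table 5 is introduced as covering primary assisted and secondary patency. Much of this stands. It lowers the weight of the Kaplan-Meier sentence and makes 10.3.2.2 the likeliest rule to be programmed. It does not remove the conflict: Table 5 has a Primary Patency column whose triggers differ from those of 10.3.2.2, the Kaplan-Meier sentence names the primary effectiveness endpoint, and rule 2 still disagrees with criterion (a).

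A reader might go further than the documents allow in four ways:

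- *That the protocol is a rival rule because it removes nobody.* Protocol section 14 leaves data-handling rules to the SAP, so its silence is not a contradiction.
- *That SAP 7.9.1.2 discards every subject with a TVR.* It covers only a TVR before the 12-month imaging window in a subject without CD-TLR, and it allows qualifying images from on or before the TVR date.
- *That keeping subjects after an off-stent TVR is the only correct choice.* The SAP gives a reason for removing them, and protocol 10.5.4 links outcome to good inflow, so treatment of an adjacent segment could plausibly affect stent patency. Keeping a patent subject also favours the device. Either choice is defensible if it is stated once.
- *That the result is fragile in general.* At the planning rate it is not. SAP 7.4.2 also plans a tipping-point analysis for missing outcomes.

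**Conclusion.** The inconsistency is real and should be reconciled. Rules 1 and 2 of SAP 10.3.2.2 and the Primary Patency column of Table 5 use different triggers; the Kaplan-Meier sentence adds a third, looser one; and rule 2 censors an event that criterion (a) counts. The root cause is that TVR is undefined while the target vessel is wider than the stent.

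The size depends on where the observed rate falls. At the planning rate it is about 0.1 percentage point per patent subject, and 29 removals would be needed to lose the objective. At the critical value, one patent subject removed loses it; one success below that value, two failures removed gain it. This rests on exact limits and on some subjects having an off-stent TVR before their 12-month image, a number the documents do not give.

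**What to change.** 1. Define TVR in the SAP, stating whether it includes re-intervention inside the stented segment.
2. State one trigger and apply it identically in SAP 7.1.3, 7.9.1.2, 10.3.2.2 rules 1 and 2, and Table 5. TLR of the stented segment is the option consistent with Table 5 and with an endpoint defined on the stent. It does not by itself align with protocol 6.3.1, which has no Missing rule for a not clinically driven TLR; that difference should be acknowledged in one sentence.
3. Count every CD-TLR within 390 days as a failure, in line with criterion (a). This removes the last sentence of rule 2 and needs a matching edit to Table 5 row 3, which can be read as covering a TLR followed by a CD-TLR.
4. Report the primary proportion under the alternative trigger (off-stent TVR subjects set to Missing) as a sensitivity analysis, with the number of subjects reclassified in each direction.
5. The 12-month data have already supported the PMA (protocol synopsis and 5.2), so a new rule would be post hoc for that test. State which rule was applied there. Use the single rule prospectively for 24- and 36-month patency, to which SAP 10.3.2.2 extends a similar convention.

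The cost is wording in four SAP places, one definition, one clarifying sentence and one extra run. No new data are needed.
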